11. APPENDICES

11.1. Statement of Obligations of Sponsor, Monitor, and Clinical Investigator

Sponsor and Monitor

If the Sponsor is not familiar with the Study Site, the Sponsor or its designated representative, will:

- A. Conduct a prestudy visit to:
 1. Establish the acceptability of the facility, the recruitment potential and the standard of patient care at this site, and record this in a written report.
 2. Discuss the proposed clinical trial with the Investigator, review the CRF requirements, and supply the Investigator Brochure and the draft protocol for review and approval.
 3. Discuss with the Investigator FDA and other regulatory requirements with respect to Informed Consent, competent authority (CA) and institutional review board (IRB)/ethics committee (EC) approval of the trial, the protocol, protocol amendments, and Informed Consent changes.
- B. Conduct periodic site visits to:
 1. Assure adherence to the protocol.
 2. Review CRFs and medical records for accuracy and completeness of information.
 3. Examine pharmacy records for documentation of quantity and date of receipt of investigational supplies, dispensation and accountability data for administration to each subject, loss of materials, contamination, and unused supplies.
 4. Record and report observations on the progress of the trial and continued acceptability of the facilities in a Site Visit Report.
 5. Review Investigator files for required documents, e.g., protocols, protocol amendments, CA and IRB/EC approvals (protocols, amendments, Informed Consent, etc.), IRB/EC charter and membership, and communications between the IRB/EC and the Investigator.

Clinical Investigator

A. IRB/EC

The Investigator must assure the monitor that the IRB/EC:

1. Meets FDA regulations as defined in 21 CFR Part 56 and other applicable ICH and GCP requirements.
2. Has authority delegated by the parent institution and found in IRB/EC by-laws, operation guidelines, or charter to approve or disapprove clinical trials and protocols, including Informed Consent Forms and other documents (protocol amendments, information to be supplied to subjects concerning Informed Consent, etc.).

3. Complies with proper personnel makeup of an IRB/EC and maintains an active up-to-date roster of all IRB/EC members participating in the meetings.
4. Convenes meetings using acceptable rules of order for making decisions, recording such decisions, and implementing them.
5. Files contain (a) documentation of its decisions such as are found in IRB/EC minutes and correspondence, (b) written guidelines or by-laws governing IRB/EC functions, (c) protocols, (d) protocol information to be supplied to the subject, (e) correspondence between the IRB/EC and the Investigator (Informed Consent Form changes, protocol amendments, etc.).

B. Informed Consent of Human Subjects.

The Principal Investigator must assure the monitor that the Informed Consent Form:

1. Meets FDA regulations as defined in 21 CFR Part 50 Informed Consent, and other applicable ICH and GCP requirements.
2. Has been approved by the IRB/EC, including, when required, information to be given to the subject regarding the trial in which s/he is enrolled.
 - a. The Informed Consent Form includes the Basic Elements and any Additional Elements necessary.
 - b. The subject and a study center representative sign the Informed Consent Form and the subject is given a copy.

C. Storage and Dispensing of Study Supplies.

The Investigator (or pharmacist or pharmacy technician) must demonstrate to the monitor that:

1. Adequate and accurate written records show receipt and disposition of all study supplies, including dates, serial or lot numbers, quantities received, and each quantity dispensed, administered, or used, with identification of each subject.
2. Purpose and reasons are given in written records for study material disposal, e.g., the amount contaminated, broken, or lost, and the quantity returned to the Sponsor.

D. Case Report Forms.

The Investigator must assure the monitor that:

1. Case report forms, when completed, accurately reflect the medical records on each subject.
2. Case report forms and medical records will be accessible to the monitor or FDA and other Regulatory inspectors during site visits.

E. Files and Records.

The Investigator must assure the quality, integrity, and content of his or her files that will be inspected by the monitor and regulatory inspectors. The files must contain, at a minimum:

1. Correspondence between the IRB/EC and the Investigator.
2. The following documents:
 - a. IRB/EC-approved protocols.
 - b. IRB/EC-approved protocol amendments.

- c. IRB/EC-approved Informed Consent Form and information supplied to the subject.
- d. IRB/EC charter, membership, and qualifications.

3. Clinical supplies:

- a. Record of receipt, date and quantity, and batch or lot number.
- b. Disposition dates and quantity administered to each subject.
- c. Inventory records.

The FDA requires retention of records for two years following the date a marketing application is approved, or for two years after the FDA is notified that the IND is discontinued if there is no marketing application. Records must be retained for a period at least as long as that specified by FDA regulations. Clinical trial related documents will be archived for at least 10 years according to national Swedish and EU regulations (LVFS 2003:3).

1. ABBREVIATIONS

Abbreviation	Definition
AE	Adverse events
ATC	Anatomical Therapeutic Chemical
b.i.d.	twice a day
BMI	Body mass index
CFB	Change From Baseline
CTCAE	Common Terminology Criteria for Adverse Events
ECG	Electrocardiogram
eCRF	Electronic case report form
EGF	epidermal growth factor
eGFR	Estimated glomerular filtration rate
FDA	Food and Drug Administration
GCP	Good Clinical Practice
ICH	International Conference on Harmonisation
IgAN	IgA nephropathy
ITT	Intent-to-treat
MCP-1	Monocyte chemoattractant protein-1
MedDRA	Medical Dictionary for Regulatory Activities
mITT	Modified intent-to-treat
PCR	Urinary protein : creatinine ratio
PD	Pharmacodynamics
PE	Physical Examination
PK	Pharmacokinetics
pP	Per protocol
PT	Preferred Term
RAAS	Renin-angiotensin-aldosterone system
SAE	Serious adverse event
SAP	Statistical analysis plan
SI	International System of Units
SOC	System Organ Class
TEAE	Treatment-emergent adverse event
TESAE	Treatment-emergent serious adverse event
WHODD	World Health Organization Drug Dictionary

2. REVISION HISTORY

This is version 0.2 of the SAP.

3. INTRODUCTION

This statistical analysis plan (SAP) is based on the clinical study protocol CL005_168, Amendment 3.0, dated 17 July 2015 and its associated electronic case report forms (eCRF).

This document describes the rules and conventions to be used in the analysis and presentation of efficacy and safety data as planned for the clinical protocol. It describes, in detail, the data and variables to be summarized and analyzed, including specifications of the analytical methods to be performed.

This SAP does not cover the statistical methods for drug concentration, pharmacokinetic parameters (PK) and pharmacokinetic/pharmacodynamics (PK/PD) analysis. These analyses will be described in a separate plan.

4. STUDY OBJECTIVES

4.1. Primary Objectives

The primary safety objective of this study is to evaluate the safety and tolerability of CCX168 in subjects with IgAN on background supportive therapy with a maximally tolerated dose of RAAS blockade.

The primary efficacy objective is to evaluate the efficacy of CCX168 based on an improvement in proteinuria.

4.2. Secondary Objectives

The secondary objectives of this study include assessment of:

1. Change in albuminuria with CCX168 treatment;
2. Change in renal function based on eGFR with CCX168 treatment;
3. Change in hematuria with CCX168 treatment;
4. Change in renal inflammatory activity based on urinary monocyte chemoattractant protein-1 (MCP 1):creatinine ratio and urinary epidermal growth factor (EGF):MCP-1 ratio with CCX168 treatment;
5. Change in serum IgA:plasma C3 ratio with CCX168 treatment;
6. Changes in pharmacodynamic markers in plasma and urine with CCX168 treatment, e.g., C3a, C5a, properdin, and sC5b-9;
7. Evaluation of the pharmacokinetic profile of CCX168 in subjects with IgAN.

5. STUDY DESIGN

5.1. General Description

This is an open-label, single arm study to test the safety, tolerability, and efficacy of CCX168 in reducing proteinuria in patients with IgAN and persistent proteinuria despite supportive therapy with a maximally tolerated RAAS blocker.

The study includes a ≤ 14 days screening period, a ≤ 4 weeks of RAAS dose titration period, a ≤ 7 days urinary PCR and eGFR eligibility confirmation period, an 8 weeks run-in period, and a 12 weeks treatment period, followed by a 12 weeks of follow-up period.

Patients who meet the inclusion criteria including

- biopsy-proven IgAN
- proteinuria > 1 g/g creatinine (by first morning urinary PCR)

and none of the exclusion criteria will be enrolled for blood pressure/RAAS blockade titration and run-in period. Patients' RAAS blocker(s) dose will be titrated to a maximally tolerated dose (MTD) to achieve a stable blood pressure target of $<125/75$ mmHg (SBP/DBP). Patients will be maintained on the stable dose of the RAAS blocker(s) for the run-in, treatment and follow-up periods. During the run-in period, patients' urinary protein: creatinine ratio will be collected and the slope over time will be calculated to form the baseline for the primary endpoint analysis. In the treatment period, patients will receive CCX168 b.i.d. The schedule of data collection is found in Study Diagram and Time and Events Table in the sections below.

5.2. Study Treatment

CCX168, 30 mg, will be administered b.i.d. during the treatment period.

5.3. Randomization Methodology

[figure not shown]
There is only one treatment group in the study. No randomization will be performed.

5.4. Stopping Rules and Unblinding

To safeguard the subject's well-being, the trial stopping criteria are set up as follows.

- If $>25\%$ of the patients ($N > 4$) have developed CTCAE (v4.03) study drug-related Grade 3+ leukopenia, neutropenia, or lymphopenia deemed possibly related to CCX168 use, the trial will be stopped.
- The Sponsor will consider stopping the study if at least one subject develops severe liver injury believed to be caused by CCX168. Severe liver injury is based on Hy's law (elevated aminotransferase of $>3 \times$ upper limit of normal [ULN], alkaline phosphatase $<2 \times$ ULN, and associated with an increase in total bilirubin $\geq 2 \times$ ULN). If any subject who receives CCX168 develops hepatic aminotransferase or total bilirubin elevations of $>3 \times$ ULN, CCX168 use will be stopped in this subject..

5.5. Study Schema

5.6. Study Procedures

The schedule of events, as outlined in the study protocol, is provided below.

SCHEDULE OF EVENTS

	Study Day ¹																
	Screening ²	Titration	Run-in			Treatment						Follow-up					
			≤ 14 days	≤ 28 days	-63	-35	-7 to -2	1 ³	8	15	29	43	57	85	113	141	169
Informed consent	X																
Demographics, medical history, prior medications	X																
Physical examination ⁴	X							X ⁵			X	X	X	X	X	X	X
Blood pressure ⁶	X	X	X	X	X, X	X	X	X	X	X	X	X	X	X	X	X	X
RAAS blocker dose titration ⁷		(X)															
RAAS blocker stable dosing at MTD			X→	→	→	→	→	→	→	→	→	→	→	→	→	→	→
Other vital signs ⁸	X							X ⁹	X	X	X	X	X	X	X	X	X
Serum pregnancy test for women of childbearing potential	X					X				X	X	X	X	X			
HIV, HBV, HCV testing	X																
Serum chemistry ¹⁰ , hematology	X							X ⁹	X	X	X	X	X	X	X	X	X
Serum creatinine (not full chemistry)			X	X	X												
Urinalysis ¹⁰	X							X ⁹	X	X	X	X	X	X	X	X	X
Urine protein and creatinine assays	X		X	X	X, X	X ⁹	X	X	X			X	X	X	X	X	X
Renal biopsy ¹¹	X													X			
Urine albumin, MCP-1, EGF, and microscopic RBC count			X	X	X	X ⁹	X	X	X			X	X	X	X	X	X
Serum IgA and plasma C3 samples								X ⁹		X		X	X	X	X	X	X
CCX168 dispensing								X ⁹	X	X	X	X	X				
CCX168 dosing 30 mg b.i.d.								X→	→	→	→	→	→	→X			
CCX168 accountability									X	X	X	X	X	X			
PD plasma sample collection ¹³								X ⁹	X	X	X		X	X	X	X	X
PD urine sample collection								X ⁹	X	X	X		X	X	X	X	X
PK plasma sample collection ¹³								X ⁹	X	X	X	X	X	X			
Concomitant medications	X	X	X	X	X, X	X ⁹	X	X	X	X	X	X	X	X	X	X	X
Adverse event assessment		X	X	X	X, X	X, X	X ⁹	X	X	X	X	X	X	X	X	X	X

¹ Visit Days 1, 8, and 15 must occur on the scheduled study days. Visit Days 29, 43, 57, and 85 may occur within a +/- 2-day window of the scheduled visit. Visit Days 113, 141, and 169 may occur within a +/- 4-day window of the scheduled visit.

² Screening must occur within a period not to exceed 14 days.

³ Start of dosing with CCX168.

⁴ Physical examination will include body weight measurement; Height will only be measured at Screening.

⁵ These procedures must be done BEFORE taking the first dose of study medication.

⁶ Blood pressure needs to be measured in the supine position after 3 minutes of rest.

⁷ Four-week dose titration period only needed for patients who are not on a maximum tolerated dose of a RAAS blocker, or stable dose of two RAAS blockers.

⁸ Assessment of heart rate and body temperature

⁹ Serum chemistry including creatinine measurements

¹⁰ Subjects will be asked to void their bladders completely, and a representative clean catch, midstream urine sample will be collected. Urinalysis includes pH, specific gravity, glucose, nitrite, ketones, bilirubin, urobilinogen, RBCs, and WBCs.

¹¹ Renal biopsy is an optional procedure for this study, except if necessary for eligibility assessment.

¹² Blood samples will be put in wet ice immediately after collection, centrifuged in a refrigerated centrifuge and plasma put at -70 °C.

¹³ PK blood sample (4 mL) will be collected prior to the morning dose on Day 1 and at 0.5, 1, 2, 3, 4, and 6 hours following dosing.

6. DEFINITIONS

Table 1. Terminology and Definition

Terminology	Definition
Age	Age is calculated as the number of full years since date of birth at the time of signing the Informed Consent Form (ICF).
Study Drug	CCX168
Study Day	The number of days relative to the very first day when the subject receives a dose of the study drug. For visits prior to the first dose of the study drug, Study Day is calculated as Visit Date minus the first dose date. For visits after the first dose, Study Day is calculated as Visit Date minus the first dose date plus 1.
Screened	Subject who has signed informed consent.
Enrolled	Subject who has entered the RAAS dose titration/run-in period
Treated	Subject who has received a dose of the study drug.
Treatment Period	From the first dose to the last dose, inclusive, of the study drug
Follow-up Period	After the last dose, exclusive, of the study drug
Completer for the treatment	Subject who has completed the 12 weeks of the treatment period with Day 85 assessment.
Completer for the study	Subject who has completed the 12 weeks of the treatment period and follow-up period.
Baseline	Generally, baseline is defined as the non-missing value collected most recent to and before the time of the very first dose of the study drug unless specified otherwise. For urinary PCR, baseline will be the geometric mean of the two measurements made in the Day -7 to -2 window plus the Day 1 (pre-dose) value. For the eGFR, urinary ACR, MCP-1:creatinine ratio, EGF:MCP-1 ratio, and microscopic RBC count, baseline will be the geometric mean of the one measurement made in the Day -7 to 2 window plus the Day 1 (pre-dose) value.
Pre-treatment Adverse Event	Adverse event starting/worsening prior to the time of the first dose of the study drug administration.
Treatment Emergent Adverse Event	Adverse event starting/worsening between the first and last dose of the study drug administration.
Post-treatment Adverse Event	Adverse event starting/worsening after the last dose of the study drug.
Prior Medication	Medication on the Prior/Concomitant Medication CRF with start date prior to Study Day 1.
Concomitant Medication	Medication collected on the Prior/Concomitant Medication CRF with end date on/after Study Day 1, including missing end date or medication ongoing.

7. EFFICACY AND SAFETY VARIABLES

All efficacy variables are derived from laboratory blood and urine samples, unless indicated otherwise.

7.1. Primary Efficacy Endpoint

- Change in slope of first morning urinary PCR (protein:creatinine ratio) from the 8-week RAAS blocker run-in period to the 12-week treatment period.

7.2. Other Efficacy Endpoints

1. Proportion of subjects achieving renal response, defined as an improvement in proteinuria based on a decrease from baseline to Day 85 in proteinuria to a level <300 mg/g creatinine and maintaining estimated glomerular filtration rate (eGFR) within 15% of baseline
2. Proportion of subjects achieving a partial renal response, defined as an improvement in proteinuria based on a decrease from baseline to Day 85 in proteinuria to a level <1 g/g creatinine and maintaining eGFR within 15% of baseline
3. Change in slope from the run-in period to the treatment period for
 - a. urinary ACR,
 - b. eGFR,
 - c. urinary MCP-1:creatinine ratio,
 - d. urinary EGF:MCP-1 ratio, and
 - e. urinary microscopic RBC counts
4. Percent change from baseline to Day 85 in
 - a. urinary PCR and
 - b. urinary ACR
5. Change from baseline (CFB) to Day 85 in eGFR
6. In patients with hematuria at baseline, the percent change from baseline in urinary RBC count
7. Percent change from baseline to Day 85 in urinary MCP-1:creatinine ratio
8. Percent change from baseline to Day 85 in serum IgA:plasma C3 ratio
9. Percent change from baseline to Day 85 in urinary EGF:MCP-1 ratio
10. Percent change from baseline in plasma and urinary biomarkers, e.g., C3a, C5a, properdin, and sC5b-9; if performed, results from these analyses will be presented in a separate report

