6.3.1. Study Day -63

The following study procedures will be performed on Day -63:

- Blood pressure in the supine position after at least 3 minutes of rest;
- Serum creatinine for an eGFR calculation;
- First morning urinary protein and creatinine measurements for a PCR calculation;
- First morning urinary albumin, MCP-1, EGF, and microscopic RBC count for ACR, MCP-1:creatinine, EGF:MCP-1 ratio, and hematuria assessment;
- Recording of changes in concomitant medication;
- Recording of all adverse events;
- The subjects will be reminded to stay on a stable dose(s) or their RAAS blocker(s), and to come back to the study center for their Study Day -35 visit.

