10.2.3. Grouping of Subjects

This is a single arm study. All subjects will be presented and summarized in the same treatment group.

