10.2.4. Definition of Baseline

For all analyses, baseline will be defined as the most recent measurement prior to the date and time of the first administration of CCX168. Baseline can be on the same day as the first dose of study medication, but prior to administration of study drug (typically the Day 1 pre-dose value). For urinary PCR, baseline will be the geometric mean (GM) of the two measurements made in the Day -7 to -2 window plus the Day 1 (pre-dose) value. For the eGFR, urinary ACR, MCP-1:creatinine ratio, EGF:MCP-1 ratio, and microscopic RBC count, baseline will be the geometric mean of the one measurement made in the Day -7 to -2 window plus the Day 1 (pre-dose) value.

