10.7.5. Percent change from baseline to Day 85 in

- a. urinary PCR and
- b. urinary ACR

Urinary PCR and ACR will be summarized with geometric mean, median, minimum, and maximum at each visit. Percent change from baseline will be based on the geometric mean ratios of Visit:Baseline. The 95% confidence interval for the geometric mean ratios will be presented.

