10.7.6. Change from baseline to Day 85 in eGFR

Estimated GFR and its change from baseline will be summarized with arithmetic mean, standard deviation, SEM, median, minimum, and maximum at each visit. The 95% confidence interval for the change will be presented.

10.7.7. In patients with hematuria at baseline, the percent change from baseline in urinary RBC count

For the purpose of analysis, urinary RBC count will be recoded as follows. None = 0.1, Occ = 0.5, 1 - 2 = 1, 3 - 5 = 3, 6 - 9 = 6, 10 - 15 = 10, 16 - 29 = 16, 30 - 49 = 30, 50 - 75 = 50, >75 = 75.

The method of summary described in Section 10.6.5 applies here.

- 10.7.8. Percent change from baseline to Day 85 in urinary MCP-1:creatinine ratio;
Percent change from baseline to Day 85 in serum IgA:plasma C3 ratio ;
Percent change from baseline to Day 85 in urinary EGF:MCP-1 ratio

The method of summary described in Section 10.6.5 applies here.

- 10.7.9. Shift in Urinary PCR, ACR, and hematuria

Shift tables will be created for urinary parameters, such as urinary PCR, ACR, and red blood cells, from baseline to each visit. The categories of interest are <300 mg/g, 301-1000 mg/g, \geq 1000 mg/g for PCR and ACR, and \leq 5 RBCs/hpf, >5 to <30 RBCs/hpf, and \geq 30 RBCs/hpf for urinary RBC count.

- 10.7.10. Percent change from baseline in plasma and urinary biomarkers, e.g., C3a, C5a, properdin, and sC5b-9

If conducted, the results will be presented in a separate report.

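### The hematuria percent-change endpoint selects subjects on the same RBC baseline that it divides by, so regression to the mean tilts the result towards an apparent fall; the size depends on a cut-off that the plan does not state

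*SAP*

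**What the plan says.** - **Endpoint.** SAP 7.2, item 6 (also Protocol 7.8, item 6): "In patients with hematuria at baseline, the percent change from baseline in urinary RBC count". Neither document says how many RBCs per high-power field count as hematuria.
- **Baseline.** SAP 10.2.4 opens with a general rule, "For all analyses, baseline will be defined as the most recent measurement prior to the date and time of the first administration of CCX168", and then gives a specific one for several markers, urinary red cells among them: "baseline will be the geometric mean of the one measurement made in the Day -7 to -2 window plus the Day 1 (pre-dose) value".
- **Effect measure.** SAP 10.7.7 refers to a Section 10.6.5, which does not exist. The matching text is 10.7.5: "Percent change from baseline will be based on the geometric mean ratios of Visit:Baseline", with a 95% confidence interval.
- **Coding.** SAP 10.7.7 replaces each RBC category by a number ("None = 0.1, Occ = 0.5, 1 - 2 = 1, 3 - 5 = 3", and so on up to 75).
- **Comparator.** SAP 10.2.3: "This is a single arm study. All subjects will be presented and summarized in the same treatment group". SAP 10.2.6 marks covariate adjustment as not applicable.
- **Earlier counts.** RBC counts are also taken on Day -63 (Protocol 6.3.1: "First morning urinary albumin, MCP-1, EGF, and microscopic RBC count for ACR") and Day -35 (6.3.2). They are not part of the baseline and are not used to form the hematuria subset.
- **Listed output.** SAP Appendix A, Table 14.2.10, gives the RBC percent change for the mITT population. Its title carries no hematuria restriction.

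**The concern.** One noisy number does two jobs: it decides who enters the analysis, and every later count is divided by it. A subject near the cut gets in when the two baseline samples happen to read high and stays out when they read low. The next independent count tends back to the subject's own level. Within the selected subset the expected ratio is therefore below 1 even if the drug does nothing, and the error always favours benefit. A control arm would show the same drift and cancel it, but this study has none.

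Change in hematuria is secondary objective 3. A reader of the percent change and its confidence interval could not separate this drift from a treatment effect.

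**Working it through.** The plan states no figure for this endpoint to reproduce; its sample-size paragraph concerns the primary slope comparison only.

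**Inputs from the documents:** two-sample geometric-mean baseline; category codes from 0.1 to 75; ratio on the geometric scale; one arm; up to about 20 subjects. The lowest RBC shift-table boundary, 5/hpf (SAP 10.7.9), is used as one possible cut.

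**Assumed, because the documents are silent:** log-normal counts, median 5-20/hpf, between-subject ln SD (sb) 1.2, within-subject ln SD (sw) 0.5-1.0, independent deviations between visits, no drug effect and no time trend.

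**Closed form, before category coding.** Let B be the ln baseline and c the cut:

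- S² = sb² + sw²/2
- a = (ln c − ln median)/S
- λ(a) = φ(a)/[1 − Φ(a)]
- mean ln ratio in the subset = −(sw²/2)/S × λ(a)

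Mid case, median 10, sw 0.7:

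- S² = 1.44 + 0.245 = 1.685, so S = 1.298.
- Cut at 6 (the lowest code above 5): a = (1.792 − 2.303)/1.298 = −0.394; λ = 0.565. Mean ln ratio = −(0.245/1.298) × 0.565 = −0.107, a false fall of 10.1%, with 65% of subjects selected.
- Cut at 1: a = −2.303/1.298 = −1.774; λ = 0.086. Mean ln ratio = −0.0162, a false fall of 1.6%, with 96% selected.

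**Simulation with the SAP's codes, no drug effect:**

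| Rule | False fall at Day 85 |
|---|---|
| Select on baseline >5/hpf, whole grid | about 4-29% |
| Same, median 10, sw 0.7 | about 12% |
| Select on baseline ≥1/hpf, whole grid | about 0-8% |
| All subjects, no selection | about 0% |
| Select on Day -63/-35, independent deviations | about 0% (within 1%) |

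How continuous counts are rounded into the categories matters a little: the mid case moves between about 11.5% and 13%, and the top of the >5/hpf range can reach about 32%.

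**Effect on the interval.** With 20 enrolled and a cut of >5/hpf, the subset holds about 9-16 subjects. The chance that the 95% interval lies wholly below 1 under no effect is then about 4-10%, instead of 2.5%.

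**Stress test of the remedy.** At median 10 and sw 0.7, let 50-80% of the within-subject variance be autocorrelated with a half-life of 2-12 weeks. Selecting on Day -63/-35 then leaves a false fall of about 1.5-6%, against about 11-17% for the planned rule. Over the main grid, 5-27% of subjects selected on Day -63/-35 have a baseline at or below 5/hpf.

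**The case against.** Four points on the other side carry weight.

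1. **The cut-off is unknown.** The 5/hpf boundary is a shift-table category, not a definition of hematuria. If any visible red cells count, nearly everyone is selected and the bias can be negligible. This stands. It limits the size but not the mechanism, and a missing cut-off in an open-label study needs repair anyway.
2. **The restriction may not be applied.** Table 14.2.10 is listed for mITT without it; run that way, there is no selection and no bias of this kind. But the title may simply be shortened, and the heading of 10.7.7 and item 6 both state the restriction. The SAP should settle which applies.
3. **The endpoint's weight is limited.** It is one of ten non-primary efficacy endpoints in a pilot, with an interval and no planned test. The RBC slope and shift analyses do not use this selection. In the mid case the bias is about 0.12 on the ln scale. With 13 subjects and an SD of the ln ratio of about 0.82, the interval half-width is about 2.18 × 0.82/√13 ≈ 0.5. This stands, and keeps the priority modest.
4. **Two samples are already averaged.** That reduces the bias but does not remove it.

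A reader might go further and infer that the reported result must be centred on a material false improvement. The documents do not support that, because without a cut-off or an RBC distribution the shift may be close to nil. Nor do they support the inference that selecting on the run-in counts abolishes the bias, since that requires independent deviations between visits.

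**Conclusion.** The point holds in direction. As item 6 and SAP 10.2.4 are written, selection and denominator share the same two samples, no comparator absorbs the drift, and the bias runs towards an apparent fall. Its size cannot be derived from the documents. Under the assumptions above it is about 4-29% with a cut of >5/hpf (about 12% in the mid case) and about 0-8% with a cut of ≥1/hpf. Confidence is high for the mechanism and low for any single figure. This is an inexpensive improvement to a non-primary endpoint and does not affect the primary PCR analysis.

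**What to change.** In SAP 10.7.7:

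- state the hematuria cut-off, for example the existing shift boundary of more than 5 RBCs/hpf;
- form the subset from the geometric mean of the Day -63 and Day -35 RBC counts;
- keep the Day -7 to -2 plus Day 1 geometric mean as the denominator;
- report the same geometric mean ratio and 95% interval in all mITT subjects alongside, which involves no selection and matches Table 14.2.10 as listed;
- point the method reference to 10.7.5.

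The cost is a few sentences, with no new samples or visits. There are two downsides. Some selected subjects (roughly 5-27% under the assumptions used) may have a baseline at or below 5/hpf, so the subset should be relabelled *hematuria during run-in* and the departure from the protocol's wording recorded in SAP Section 11. And if a subject's deviations persist over weeks, about 1.5-6% of false fall can remain. The all-mITT result is the safer reference.
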